4.0 Study Endpoints

*4.1 Describe the primary and secondary **study** endpoints. See links below for discussion of study endpoints and how they may differ from study*

objectives. These are most common in clinical trials but are sometimes applicable to other types of biomedical research, as well as social, behavioral, or educational research. See link below for a discussion.

https://docs.google.com/document/d/1Wocz7K7a0hCQJPP0_khh5l1SQQjhGDDGHzcOPRHR5Tw/edit?usp=sharing

Primary endpoint will be the Pearson's correlations between the following variables:

- Mobility in X, Y, and Z planes each with pre-ejection period (PEP)
- Mobility in X, Y, and Z planes each with phasic electrodermal activity (EDA)

Secondary endpoint will be the Pearson's correlations between the following variables:

- Mobility in X, Y, and Z planes each with HF-HRV
- PEP and Subjective Unites of Distress Scale (SUDS)
- EDA and SUDS
- HF-HRV and PEP during one minute intervals where mobility is transitioning

- 4.2 *Describe any primary or secondary **safety** endpoints. These should be included for all studies that are greater than minimal risk. (Minimal risk: The probability and magnitude of harm or discomfort anticipated in the research that are not greater in and of themselves than those ordinarily encountered in daily life or during the performance of routine physical or psychological examinations or tests.):*

In order to minimize dangers associated with disoriented movement in the VR environment, one research assistant will be assigned the role of participant spotter, attending to any unsafe movements that participants may attempt while navigating their virtual environment.

Experiencing VR can increase the risk of dizziness or nausea because of the discrepancy between the actual and the virtual environment. The consent form includes a description of this possibility and how the participant can address it if they do not have tolerance of such symptoms.

The probability of psychological discomfort is assessed to be the same or less than that of watching a horror movie or playing a horror video game.

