5.0 Study Design and Statistical Analysis Plan

- 5.1 *Describe the basic study design/approach (e.g., qualitative study using five focus groups of first year students to describe assimilation into the university community; randomized controlled trial of a behavioral change intervention to increase dietary intake of whole grains; pre- post-test evaluation of new pedagogical techniques to improve adult literacy):*

This will be a quantitative study examining variables indexing physiology, mobility, and subjective experience of participants as they are exposed to stimuli designed to move them through stages of the defense cascade.

- 5.2 *Describe corresponding data analysis plan/approach (e.g., content analysis of focus group transcripts; descriptive analysis followed by linear regression modeling; nonparametric analysis of pre- and post-test measures):*

Data will be analyzed using Pearson's correlations to examine degree of correspondence between primary variables of interest that index mobility, SNS, and PNS activation, as well as SUDS. Additionally, as time allows, moderation analysis will be conducted to determine if higher scores on trauma, PTSD, dissociation, anxiety, and BIITS phobia affect the overall patterns observed in the primary variables of interest.

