The BioNomadix Non-Invasive Cardiac Output system will be used to gather ICG data, which provides one of two inputs to the calculation of PEP, an estimate of SNS control of the heart. The Biopac ECG100C and Biopac RSP100C and/or the BioNomadix RSP & ECG System will be used to gather respiration and ECG data, which provides the second of two inputs to the calculation of PEP. It is also used to calculate HF-HRV, an estimate of PNS control of the heart. The Biopac Tri-axial Accelerometer and/or the BioHarness Physiology Monitoring System and/or the BioNomadix Accelerometer System will be used to calculate participant mobility in X, Y, and Z planes. Finally, the Biopac EDA100C and/or the BioNomadix PPG & EDA System will be used as a second estimate of SNS activation using galvanic skin response, an SNS index not influenced by the cardiac system. Uncertainty about which units will be used (the "and/or" language above) are due to uncertainty at the time of this application about whether the BioNomadix units will be funded by pending applications for scholarship and lab funds. Nevertheless, all aforementioned units will be used in accordance with their approved and attended purposes.

Two Microsoft webcams will be used to collect video footage of the participants from two angles: one will record facial expressions, while the other will record from the participant's side for behavioral coding to assess degree to which the participant is exhibiting approach versus avoidance behavior.

A noise-cancelling wireless headset will be used to deliver the audio portion of the video clips and to deliver a 98 decibel burst of white noise with 0 ms rise time and 750 ms duration.

A vibrational unit will be used to deliver a 5 volt vibration to the neck of the participant. This voltage is roughly three times the intensity of the vibration delivered by a standard smart phone in "vibrate" mode.

An Oculus Quest or Oculus Go headset will be used to present the Virtual Reality portion of the experiment to participants.

7.4 If the drug is investigational (has an IND) or the device has an IDE or a claim of abbreviated IDE (non-significant risk device), include the following information:

- Identify the holder of the IND/IDE/abbreviated IDE.
- Explain procedures followed to comply with sponsor requirements for FDA regulated research for the following:

FDA Regulation	Applicable to:		
	IND Studies	IDE studies	Abbreviated IDE studies

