11.0 Study Timelines

11.1 Describe:

- *The duration of an individual subject's participation in the study (for example, 1 hour, 2-4 weeks, 3-5 years).*
- *The amount of time expected to enroll all study subjects (weeks, months, years, etc.)*
- *The amount of time expected for the investigators to complete this study including primary data analyses.*

Each subject's participation is estimated to last 3.5 hours, including 1.5 hours for the online prescreen and 2 hours for the in-lab portion. A target of 85 subjects will be sought. It is estimated that it will take a maximum of 1 year to enroll all study subjects with a goal of completing enrollment within 6 months. Primary data analysis will be conducted as data is acquired and is expected to be completed within the same 1 year period.

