14.0 Number of Subjects

14.1 *Indicate the total number of subjects to be enrolled and how this number was determined (e.g., sample size calculation [show], number of available subjects in a finite pool, number of tests funding award would allow):*

This study will seek to enroll 85 participants. A power analysis was calculated using the G*Power applet (Faul et al., 2007) to determine required sample size for a target correlation of 0.3. With $\alpha = 0.05$ and $\beta = 0.20$, the target effect size requires a sample size of at least 85 participants. It is estimated that 85 out of the 100 participants completing online screening will be in compliance with abstention requirements

14.2 If this is a multi-site study, indicate the number of subjects to be enrolled at this site and the total to be enrolled from all sites:

N/A

14.3 If applicable, indicate the number of potential subjects you expect to screen for enrollment, and the number of subjects you will need to complete the research procedures:

It is estimated that 200 subjects will be screened for enrollment in order to obtain 100 subjects to invite to the lab. Of these, we need 85 participants to follow abstention requirements and complete the research procedure.

14.4 If the study has more than one procedure, indicate the total number of subjects to undergo each procedure separately:

N/A

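### The sample size of 85 is powered for one correlation, but the primary endpoint is six unranked correlations with no success or multiplicity rule

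*Protocol*

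**What the plan says.** - **Endpoint (Protocol 4.1).** The primary endpoint is a set of Pearson correlations in two lines: "Mobility in X, Y, and Z planes each with pre-ejection period (PEP" and "Mobility in X, Y, and Z planes each with phasic electrodermal activity (EDA". Three axes by two indices is six correlations. None is ranked, and the section does not say whether one, some or all must be significant.
- **Hypothesis (2.2).** It concerns mobility as a single construct and is directional: positive with sympathetic activation.
- **Analysis (5.2).** "Data will be analyzed using Pearson's correlations to examine degree of correspondence between primary variables of interest". No multiplicity rule is given.
- **Sample size (14.1).** The calculation was done "to determine required sample size for a target correlation of 0.3", at alpha 0.05 and beta 0.20, and concludes that "the target effect size requires a sample size of at least 85 participants". Sidedness is not stated.
- **Timing (11.1).** "Primary data analysis will be conducted as data is acquired". No number of looks, stopping rule or use of early results is described.
- **Devices (7.3).** "The Biopac Tri-axial Accelerometer and/or the BioHarness Physiology Monitoring System and/or the BioNomadix Accelerometer System will be used to calculate participant mobility" on the three axes.

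**The concern.** The study is sized for one test, while its primary endpoint contains six. With no stated rule, a significant result on any one axis with either index could be offered as support for the mobility hypothesis, at a false-positive risk well above 5%. If the six are adjusted for, or all are required, the 80% in 14.1 no longer describes the power for each correlation or for the full set. Choosing the axis or index that counts after seeing results could not be repaired later. A separate analysis plan could add a multiplicity rule, but the number of participants is fixed in the protocol, so that rule alone would not restore the power.

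**Working it through.** **Inputs.** r = 0.30, alpha = 0.05, power 0.80 and N = 85 (14.1); six primary correlations (4.1). Two-sided testing is inferred: across standard methods the two-sided answer is 82 to 85 and the one-sided answer 64 to 68.

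**1. The plan's own figure.** Fisher z: N = ((z(1−α/2) + z(power)) / atanh(r))² + 3 = ((1.960 + 0.842) / 0.3095)² + 3 = 84.93, so 85. Power at 85 is Φ(0.3095 × √82 − 1.960) = Φ(0.843) = 80.0%. The figure is right for one two-sided test.

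**2. Any of six, each at an unadjusted 0.05.** If independent, the familywise error is 1 − 0.95⁶ = 26.5%. Counting only significant results in the predicted direction, it is 1 − 0.975⁶ = 14.1%. Power per correlation stays at 80%.

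**3. Bonferroni over six (0.05/6 = 0.00833).** Power per correlation at N = 85 is Φ(2.803 − 2.638) = 56.5%. For 80%, N = ((2.638 + 0.842) / 0.3095)² + 3 = 129.4, so 130.

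**4. All six required at 0.05.** No familywise inflation. With independent tests, joint power is 0.80⁶ = 26.2%.

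**5. Dependence.** The documents give no correlations among axes or between PEP and EDA, so these are assumed. Simulation used multivariate normal data, n = 85, 20,000 runs; the power columns set all six true correlations to 0.30:

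| Among axes / PEP with EDA | Any-of-six error, unadjusted | Joint power, all six at 0.05 | Power per correlation, Bonferroni | Power for at least one, Bonferroni |
|---|---|---|---|---|
| 0 / 0 | 25.9% | 28.6% | 56.7% | 99.2% |
| 0.3 / 0.3 | 24.5% | 36.6% | 56.8% | 97.3% |
| 0.5 / 0.3 | 23.2% | 41.5% | 56.6% | 94.7% |
| 0.7 / 0.5 | 19.2% | 50.4% | 56.7% | 89.4% |
| 0.9 / 0.7 | 13.6% | 61.8% | 57.1% | 80.1% |

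A separate simulation counting only the predicted direction gave about 12% with axes correlated 0.6 and about 9% at 0.8.

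**6. Two tests instead of six.** At 0.025, power per correlation is Φ(2.803 − 2.241) = 71.3%. The smallest r with 80% power is tanh((2.241 + 0.842) / √82) = 0.328, and N for 80% at r = 0.30 is 103. Holm does better than its first step. If both effects are 0.30 and the tests independent, power per correlation is 0.713 + (0.800 − 0.713) × 0.713 = 77.5%.

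**The case against.** Several stronger readings are tempting, and the protocol does not support them.

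- **Each correlation is tested at 0.05.** A reader might infer this, but alpha appears only in the power calculation, and 5.2 speaks of examining correspondence. The error figures are what unadjusted testing would give; the protocol does not state that testing.
- **Alpha and power both fail.** They do not fail together under one rule at a single analysis. Unadjusted testing keeps 80% power per correlation, while Bonferroni and all-of-six keep the error rate. Which property is lost depends on a rule not given.
- **No rule can work.** One can, in part. If success means at least one of six after Bonferroni, and all six true correlations are 0.30, simulated power is 80% to 99%. That rests on every axis and both indices carrying the full effect, and any particular correlation is still detected only 56.5% of the time. The protocol does not state this rule.
- **Analysis during accrual inflates error.** Section 11.1 is a timeline sentence. It describes no stopping and no claim from early results, and the target stays at 85. Looks that drive no decision do not change the final test, so no inflation figure belongs here.
- **The axes carry no separate question.** Section 7.3 leaves the accelerometer open and the protocol does not fix axis orientation. However, 8.1 codes movement toward and away from the stimulus, so direction is of interest. A combined index is one option and is not required.

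It is also fair that 26.5% counts results in either direction although the hypothesis is directional, and that this is a minimal-risk thesis study. Neither removes the mismatch between one powered test and six primary ones.

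**Conclusion.** The point holds as a mismatch between 4.1 and 14.1. The 85 is correct for one two-sided correlation of 0.30 tested once. For six unranked primary correlations with no success rule, the plan does not secure both 5% familywise error and 80% power for each correlation or for the full set.

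The size depends on the missing rule: up to 26.5% familywise error unadjusted if independent (about 14% to 26% under the dependence assumed, about 14% or less in the predicted direction), 56.5% power per correlation under Bonferroni, or about 26% to 62% joint power if all six are required. These figures assume two-sided tests, true correlations of 0.30 for the power values, and inter-variable correlations that the protocol does not give.

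**What to change.** Before any results are seen, choose one of two routes.

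1. **One primary correlation.** Name it in 4.1 and move the other five to secondary or descriptive. Section 14.1 stands: 85 participants, 80% power.
2. **Two primary correlations.** Reduce mobility to one pre-specified index (for example the vector magnitude of the three axes), test it against PEP and phasic EDA with Holm at overall 0.05, and report axis-specific results as descriptive. Restate 14.1 as at least 71% power per correlation at r = 0.30 (about 77% under Holm if both effects are 0.30 and the tests independent), or as 80% at r = 0.33 at the 0.025 step. Restoring 80% at r = 0.30 at that step would take 103 completers, more than the 100 planned lab invitations.

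Under either route, add to 11.1, as a precaution, that only signal scoring and quality control run during enrolment and that the primary correlations are computed once, after enrolment closes.

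The cost is wording in 4.1, 11.1 and, for the second route, 14.1. The second route also states a less favourable power and makes the axis detail descriptive.

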1.0 Study Summary

Study Title	Defense Cascade: Physiology, Mobility, and Subjective Experience
Study Design	In-lab virtual reality (VR) stimuli will be presented for this psychophysiology study with online prescreen. Data will be analyzed using correlational analyses and OLS regression measuring mobility, SNS activation, PNS activation, and SUDS ratings. Moderation will be tested based on scores on anxiety, trauma, dissociation, and interoceptive awareness.
Primary Objective	Complete Master's thesis requirements for [name] investigating whether patterns of mobility map to physiological patterns and subjective experience when engaged in the defense cascade.
Secondary Objective(s)	I plan to submit a paper for publication in psychology peer-reviewed research journal as well as to use the data for poster presentations at conferences such as the Society for Psychophysiological Research.
Study Population	Young adults
Sample Size	200 for online prescreen, 100 to be invited to lab
Research Intervention(s)/ Investigational Agent(s)	Research intervention/stimulus will be a series of videos and experiences all presented in a VR environment, with peripheral audio and tactile enhancement. Investigational agents will include surveys, collection of psychophysiological measures including ECG, ICG, EDA, and accelerometry, behavioral observations from participant video footage, and post-hoc interviews with participants.
Study Duration for Individual Participants	1.5 hours for online prescreen, 2 hours for in lab; total of 3.5 hours
Acronyms and Definitions	
VT: Virginia Tech VR: Virtual Reality MBL: Mind-Body Lab ECG: ElectroCardioGram ICG: Impedance CardioGraphy EDA: ElectroDermal Activity PEP: Pre-Ejection Period HF-HRV: High-Frequency Heart Rate Variability PTSD: PostTraumatic Stress Disorder ANS: Autonomic Nervous System SNS: Sympathetic Nervous System PNS: Parasympathetic Nervous system SUDS: Subjective Units of Distress Scale

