2.0 Objectives

2.1 *Describe the purpose, specific aims, or objectives of this study:*

The objectives of this study are to map patterns of mobility to patterns of physiology and self-reported subjective experience during a perceived threat experience.

2.2 *State the hypotheses to be tested:*

Mobility will be moderately positively correlated with SNS activation and moderately negatively correlated with PNS activation.

Transitions in mobility will be supported by ANS coactivation.

SNS activation will be moderately positively correlated with SUDS scores.

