Changes in mobility appear to be supported by the autonomic nervous system (ANS), which engages the sympathetic nervous system (SNS) to power mobile defenses (Cannon, 1932; Lang, Bradley, & Cuthbert, 1997) and the parasympathetic nervous system (PNS) for immobile defenses (Öst 1984; Kleinknecht, 1987; Bracha, 2004). A more exacting study of the literature suggests that changes in mobility are supported by coactivation of the SNS and PNS (Löw, Lang, Smith, & Bradley, 2008; Roelofs, Hagedaars & Stins, 2010), a finding that requires replication to validate.

ANS coactivation has been characterized as a “positive predictor of health” (Berntson, 2019). It appears to support oxytocin uptake, but only among socially-connected participants. Lonely participants given oxytocin showed an increase only in SNS activation (Norman et al., 2011). ANS patterns bear further research, revealing adaptive responding in times of danger and safety.

I propose to investigate the mobility and autonomic correlates of the defense cascade, and to examine a self-report measure of subjective experience that could be leveraged in both research and clinical settings.

3.2 *Describe any relevant preliminary data:*

N/A

3.3 *Based on the existing literature, provide the scientific or scholarly rationale for and significance of your research and how will it add to existing knowledge:*

The defense cascade illustrates that defensive behavior is more than just “fight or flight” - these mobile defenses are but two of six stages. The remaining four stages are immobile defenses, each serving a unique purpose: avoiding detection, minimizing predatory aggression, reducing blood loss, and conserving resources. Yet defensive behavior is too often conceptualized as a set of mobile behaviors - "immobile defense" is viewed as an oxymoron. This view has pervaded American culture,

celebrating “action heroes” and stigmatizing victims of violence who did not fight back, mistakenly implying that an absence of mobility is an absence of defense.

Research into human defensive and survival behavior provides clues about both psychopathology and resilience. Freeze characterizes transition from calm to anxious states. The mobile defenses of flight and fight underlie stress and anxiety including most phobias (Hoehn-Saric & McLeod, 1988), as well as hyperarousal in PTSD (Morris & Rao, 2013).

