7.0 Study Intervention(s)/Investigational Agent(s)

7.1 *Describe the study interventions (including behavioral interventions) and/or investigational agents (e.g., drugs or devices) to be used in this study. Consider each of the items listed below:*

- *Drug/Device Handling: If the research involves drugs or devices, describe your plans to store, handle, and administer the drugs or devices so that they will be used only on subjects, and only by authorized investigators.*
- *Describe whether any of the following will be used: microwaves, X-rays, DEXA scans, general anesthesia, or sedation*

- *If control of the drugs or devices used in this protocol will be accomplished by following an established, approved organizational SOP (e.g., Research Pharmacy SOP for the Control of Investigational Drugs, etc.), please reference the SOP in this section.*

This study's intervention will be a series of video clips projected in a VR environment, combined with a threat scenario designed uniquely for the VR environment. Additional interventions will include an audio white noise stimulus, a tactile vibrational stimulus, and a post-stimulus debrief. Video clips will be viewed as if on a projector within the VR environment and will include: (1) an approximately 3-minute instructional video on the use of the SUDS rating system, (2) an approximately 4-minute non-narrated video depicting marine life in a sunny, non-threatening situation accompanied by a soothing musical score, and (3) a portion of the threat scenario begins with images projected on the virtual projector. Both (1) and (2) are vanilla baseline clips, designed to measure physiological and mobility responses in a non-threatening situation as a baseline. The unique VR scenario begins again by a presentation of stimuli as if projected on a movie screen within the VR environment. The culmination of this threat scenario depicts a creature emerging from the projected movie screen and appearing to approach the participant in the VR environment.

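### The only endpoint for the coactivation hypothesis, a Pearson correlation of HF-HRV with PEP inside transition minutes, does not show whether coactivation is specific to transitions

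*Protocol*

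**What the plan says.** The second of the three hypotheses in Protocol section 2.2 reads "Transitions in mobility will be supported by ANS coactivation". Section 3.1 gives its basis, that "changes in mobility are supported by coactivation of the SNS and PNS", and says this finding needs replication.

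Section 4.1 fixes the statistic: "Secondary endpoint will be the Pearson's correlations between the following variables". The last item in that list is "HF-HRV and PEP during one minute intervals where mobility is transitioning". No other endpoint addresses coactivation.

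Section 5.2 adds no level comparison: "Data will be analyzed using Pearson's correlations to examine degree of correspondence between primary variables of interest", followed by moderation by questionnaire scores if time allows. The Study Summary mentions "correlational analyses and OLS regression measuring mobility, SNS activation, PNS activation, and SUDS ratings", but gives no model and no transition term.

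Section 7.3 describes the "calculation of PEP, an estimate of SNS control of the heart" and names HF-HRV as the parasympathetic index. Section 7.1 provides two neutral clips "designed to measure physiological and mobility responses in a non-threatening situation as a baseline", but the coactivation endpoint does not use them.

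**The concern.** On its natural reading, coactivation at transitions is a statement about levels: both branches are more active when mobility changes than when it does not. The planned statistic discards levels, because it centres each variable on its own mean, and it looks only at transition minutes. Two errors follow. A real joint rise can leave the correlation at zero. A correlation that exists at all times, for instance from stable differences between people, can be taken for something that happens at transitions.

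The Protocol fixes both the statistic and the data window, so this is more than a detail left to an analysis plan. At stake is the interpretability of the sole test of one of three hypotheses.

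**Working it through.** **The Protocol's own figure.** Section 14.1 gives a target correlation of 0.3, α = 0.05, β = 0.20 and N = 85. By Fisher's z, two-sided: n = ((1.960 + 0.842) / atanh 0.3)² + 3 = (2.802 / 0.3095)² + 3 = 84.93, so 85. The figure reproduces. (One-sided would give 68.)

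**Invariance.** For any constants a and b, corr(X + a, Y + b) = corr(X, Y). A rise of a in HF-HRV and a change of b in PEP, the same for everyone, leaves r where it was. Subtracting each person's baseline first does not bring the mean shift back, because r centres the data again.

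**Simulation.** The Protocol gives no shifts, variances or correlations, so these are assumptions: 85 participants, one pair of values per person and state, unit variances, a correlation of 0.5 between states within person, and 4,000 runs per scenario. Coactivation is coded as HF-HRV up and PEP down. The paired column is the share of runs in which both transition versus non-transition contrasts are significant in that direction.

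| Scenario | Mean r | Pearson significant | Both paired contrasts |
|---|---|---|---|
| Both branches up 0.5 SD, no correlation | 0.00 | 4.3% | 99% |
| Both branches up 1 SD, no correlation | 0.00 | 5.1% | about 100% |
| No shift, r = −0.3 in both states | −0.30 | 80% | 0.3% |
| No shift, r = −0.3 at transitions only | −0.30 | 82% | 0.2% |
| Both branches up 0.5 SD, r = +0.3 in both states | +0.30 | 80%, none of it negative | 99% |

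The third and fourth rows show the cost of having no comparator: a correlation present all the time and one confined to transitions give practically the same result.

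**Response strength that differs between people.** Let a person's response be g, with mean μ and standard deviation s, added to HF-HRV and subtracted from PEP, each with unit residual variance and no other correlation. Then r = −s² / (1 + s²), and μ drops out.
- s = 0.25: r = −0.0625/1.0625 = −0.06
- s = 0.5: r = −0.25/1.25 = −0.20
- s = 0.65: r = −0.4225/1.4225 = −0.30

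With μ = 0.5, the simulated rejection rates in the coactivation direction are 8%, 45% and 81%. With μ = 0 and s = 0.65 the rate is 80%. The test follows the spread of the response, not its level.

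**Power of a within-participant contrast, n = 85, two-sided 0.05.** The noncentrality is d√85, with d the mean change divided by the standard deviation of the change.
- d = 0.3: 0.3 × 9.22 = 2.77, power about 0.78. If both contrasts must be significant and are independent: 0.78 × 0.78 = 0.61.
- d = 0.5: 0.5 × 9.22 = 4.61, power about 0.995. Both: 0.995 × 0.995 = 0.99.

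**The case against.** A reader might infer that the endpoint can never detect coactivation. The documents do not support that. Blindness is exact only for a shift that is the same throughout. If strength varies between people, a negative correlation can appear, with 8% to 81% rejection in the cases above. What remains is that such a correlation does not show a mean rise and cannot be tied to transitions.

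Section 4.1 does not say whether r is taken across participants or across minutes within a participant. The explanation by stable differences between people applies to the former or to pooled data. A within-person r would register the branches rising and falling together, but it would still miss a constant shift and still lack a comparator.

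The Protocol nowhere defines coactivation as both levels raised relative to other times, and section 5.2 speaks of correspondence. The level reading is an interpretation, though a well-founded one: section 3.1 ties coactivation to changes in mobility and sets it against a response in which only the sympathetic branch increased.

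A reader might also infer that a positive r will be read with the wrong meaning. The Protocol states neither the direction of PEP nor an expected sign for this correlation, so no misreading is written into it. That PEP shortens as sympathetic drive rises is an assumption from general physiology. Stating the direction is a clarification, not a correction.

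Finally, the missing comparator is a gap in the endpoint and not in the planned recordings, which include baseline clips.

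**Conclusion.** The point holds in a limited form. As specified, the endpoint is unaffected by a uniform rise in both branches, responds only to covariation in responses or to stable differences between people, and has no non-transition comparator. Neither a significant nor a null r therefore answers whether coactivation is specific to transitions.

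The invariance is exact. The rejection rates rest on the assumed shifts, variances and correlations and serve as illustration. The conclusion also takes coactivation to mean raised activity in both branches.

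This should be fixed, but it concerns the last-listed secondary endpoint. It would be wrong to infer that the study's main results are compromised: the correlations of mobility with PEP and with EDA, and the calculation behind N = 85, are untouched.

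**What to change.** Keep the correlation as a descriptive result if wanted. Make the test of the coactivation hypothesis a within-participant comparison of transition with non-transition minutes, as follows:

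- Classify each minute from accelerometry alone, by a rule written down in advance.
- Analyse HF-HRV and PEP separately, for example in a mixed model with a participant effect and a term for stimulus phase. Transition minutes may cluster in the threat scene, and without that term transition and scene are confounded.
- Conclude coactivation only if both indices move towards greater activation, and say whether each must be significant or only in the right direction.
- State the expected direction for PEP.

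The change needs wording and analysis code only, because the signals are already planned. There are three small costs. The analysis is longer. Participants without transition minutes contribute little, which matters because subjects are told to stay seated (section 8.3) and may be withdrawn if not still enough (section 16.1). And power at d = 0.3 falls from about 78% to about 61% if both contrasts must be significant; these figures assume that all 85 participants contribute both kinds of minute.
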